7.1.7.2. Study Drug Related Injection Site Induration and Nodules

Percentage of ongoing and resolved study drug related injection site induration will be summarized for each SC injection (eg, Day 15, Week 28, and Week 54) and the overall at both subject-level and event-level.

For the subject-level summary, if a subject had more than one injection site indurations, the subject will be counted in the “Ongoing” category unless all study drug related injection site induration events have been resolved.

For the event-level summary, duration of the resolved events will be summarized using descriptive statistics.

Study drug related injection site nodules will be summarized in the same manner as defined for study drug related injection site induration.

A by-subject listing for study drug related injection site induration and nodules and the corresponding duration will be provided.

7.2. Laboratory Evaluations

Laboratory data collected during the study will be analyzed and summarized using both quantitative and qualitative methods. Summaries of laboratory data will be provided for the Safety Analysis Set and will include data collected up to the last exposure date for subjects who have permanently discontinued study drug, or all available data at the time of the database snapshot for subjects who were ongoing at the time of an interim analysis. The analysis will be based on values reported in conventional units. When values are below the LOQ, they will be listed as such, and the closest imputed value will be used for the purpose of calculating summary statistics as specified in Section 3.7. Hemolyzed test results will not be included in the analysis, but they will be listed in by-subject laboratory listings.

Calcium Corrected for Albumin

Calcium corrected for albumin will be calculated and summarized for the study. The following formula will be used when both serum calcium and albumin results for a given blood drawn are available and serum albumin value is < 4.0 g/dL.

Calcium corrected for albumin (mg/dL) = serum calcium (mg/dL) + 0.8 × (4.0 – albumin (g/dL))

Toxicity grading for calcium will be applied based on the corrected values.

Estimated Glomerular Filtration Rate

The following formulae will be used to calculate the estimated glomerular filtration rate using Cockcroft-Gault formula (eGFR_{CG}):

$$\text{eGFR}_{\text{CG}} \text{ (mL/min)} = [(140 - \text{age (yrs)}) \times \text{weight (kg)} \times (0.85 \text{ if female})] / (\text{SCr (mg/dL)} \times 72),$$

where weight is total body mass in kilograms and SCr is serum creatinine.

Low-Density Lipoprotein

The following formulae will be used to calculate the low-density lipoprotein (LDL) using Friedewald formula when cholesterol, high-density lipoprotein(HDL), and triglyceride for a given blood drawn are available:

$$\text{LDL (mg/dL)} = \text{total cholesterol (mg/dL)} - \text{HDL (mg/dL)} - \text{triglyceride (mg/dL)}/5;$$

The fourth generation LDL is calculated from above Friedewald formula. The third generation LDL is a direct measurement from blood drawn. Both generations of LDL will be listed in the listing. Only fourth generation LDL calculated from the Friedewald formula will be used for analysis.

A by-subject listing for laboratory test results will be provided by subject ID number and visit in chronological order for hematology, serum chemistry, and urinalysis separately. Values falling outside of the relevant reference range and/or having a severity grade of 1 or higher on the Division of AIDS (DAIDS) Table for Grading the Severity of Adult and Pediatric Adverse Events, Version 2.1 dated July 2017, will be flagged in the data listings, as appropriate.

No formal statistical testing is planned.

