6.5.1. Blood Samples

Blood sample collection for the following laboratory analyses will be performed at every visit, unless specified:

- Serum pregnancy test for all women (**Screening only**)
- Serum follicle-stimulating hormone (FSH) test (FSH test is required for women who are < 54 years old and have stopped menstruating for ≥ 12 months but do not have documentation of ovarian hormonal failure) (**Screening only**)
- Chemistry profile: alkaline phosphatase, AST, ALT, gamma-glutamyltransferase (GGT), total bilirubin, direct and indirect bilirubin, total protein, albumin, lactate dehydrogenase (LDH), creatine phosphokinase (CPK), bicarbonate, blood urea nitrogen (BUN), calcium, chloride, creatinine, glucose, lipase, magnesium, phosphorus, potassium, sodium, uric acid
CCI
- Nonfasting lipid panel: total cholesterol, high-density lipoprotein (HDL), direct low-density lipoprotein (LDL), and triglycerides **CCI**
- Estimated GFR **CCI** according to:
 - Cockcroft-Gault formula for Creatinine clearance for participants ≥ 18 years of age

Male:
$$\frac{(140 - \text{age in years}) \times (\text{weight in kg})}{72 \times (\text{serum creatinine in mg/dL})} = \text{CLcr (mL/min)}$$

Female:
$$\frac{(140 - \text{age in years}) \times (\text{weight in kg}) \times 0.85}{72 \times (\text{serum creatinine in mg/dL})} = \text{CLcr (mL/min)}$$

- Hematology profile: complete blood count (CBC) with differential and platelet count
CCI [REDACTED]
- CD4+ cell count CCI [REDACTED]
- Plasma HIV-1 RNA CCI [REDACTED]
- HIV-1 genotype and phenotype at Screening visit and any subsequent visit with virologic failure (described in Section 6.7)
- HBV serologies (HBV surface antigen, HBV core antibody, HBV surface antibody) (Screening only)
- HCV antibody serology (Screening only)

[REDACTED]

- Plasma storage samples for additional safety and virology testing (HIV-1 genotype and phenotype) CCI [REDACTED]

6.5.2. Pharmacokinetic Assessments:

For Treatment Groups 1 and 2:

Plasma PK sampling will occur relative to dosing of GS-6207 at the following time points for all participants:

- Days 1, 2, and 8:
 - Predose (within 30 minutes of dosing)
 - A single timed PK sample between 1 and 6 hours postdose

[REDACTED]

- At Day 15 and at all visits with GS-6207 SC injections, including when GS-6207 SC injection is resumed after the Oral Bridging Visits, if applicable: A single predose PK sample will be collected

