- c Assessments will be performed post Week 80 (Week 90, Week 106, Week 116, Week 132, Week 142) and will continue to alternate between every 10 weeks and every 16 weeks with the visit window ±6 days.
- d Only applicable to participants who require oral weekly bridging if an SC injection of GS-6207 cannot be administered for any reason within the protocol visit window.
- e Participants may be required to return to the clinic for a 30, 90 and 180-Day Follow-Up Visit after Early Termination visit as noted in Section 6.4.1

- f Within 72 hours of permanently discontinuing study. Counsel participant regarding the importance of continuing a complete ARV therapy in accordance to standard of care and refer participant to an appropriate HIV treatment facility.
- g Complete physical exam is only required at Week 28
- h Symptom directed physical to be completed at Weeks 4, 10, 16, and 22, as necessary
- i Vital signs – blood pressure, pulse, respiration rate, temperature, and weight
- j Hematology: CBC with differential and platelet count
- k Chemistries: Alkaline phosphatase, AST, ALT, GGT, total bilirubin, direct and indirect bilirubin, total protein, albumin, LDH, CPK, bicarbonate, BUN, calcium, chloride, creatinine, glucose, lipase, magnesium, phosphorus, potassium, sodium, and uric acid. eGFR according to the Cockcroft-Gault formula
- l Fasting is not required for the lipid panel
- m Urinalysis and Urine Chemistry: including color & clarity, specific gravity, pH, glucose, ketones, bilirubin, urobilinogen, blood, nitrite, leukocyte esterase and microscopic (if microscopic elements are seen), urine protein, albumin, creatinine, phosphate, calcium, magnesium and uric acid
- n Women will have a serum test performed at Screening. Urine pregnancy test will only be done for women of childbearing potential. In Treatment Groups 1 and 2, urine pregnancy tests should be confirmed to be negative prior to subcutaneous GS-6207 administration. If any pregnancy test is positive, study drug should be immediately interrupted, and participant should come to the site for serum pregnancy test.
- o FSH test is required for women who are <54 years old and have stopped menstruating for ≥ 12 months but do not have documentation of ovarian hormonal failure.

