7.2.1. Summaries of Numeric Laboratory Results

Descriptive statistics will be provided by treatment group for selected laboratory test as follows:

- Baseline values
- Values at each postbaseline visit
- Change from baseline at each postbaseline visit

A baseline laboratory value will be defined as the last measurement obtained on or prior to the date/time of first dose of study drug. Change from baseline to a postbaseline visit will be defined as the visit value minus the baseline value. The mean, median, Q1, Q3, minimum, and maximum values will be displayed to the reported number of digits; SD values will be displayed to the reported number of digits plus 1.

Median (Q1, Q3) of the change from baseline values for these selected laboratory tests will be plotted by treatment group and visit.

In the case of multiple values in an analysis window, data will be selected for analysis as described in Section 3.8.3.

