7.2.2. Graded Laboratory Values

The DAIDS Table for Grading the Severity of Adult and Pediatric Adverse Events, Version 2.1 dated July 2017, will be used to assign toxicity grades (0 to 4) to laboratory results for analysis. Grade 0 includes all values that do not meet the criteria for an abnormality of at least Grade 1. For laboratory tests with criteria for both increased and decreased levels, analyses for each direction (i.e., increased, decreased) will be presented separately.

For triglycerides, LDL (4th generation), and cholesterol, the toxicity grading scale is for fasting test values, so nonfasting lipid results (or lipid results without a known fasting status) will not be graded or summarized by toxicity grades.

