7.8. Changes From Protocol-Specified Safety Analyses

No change from protocol-specified safety analyses is planned.

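### Numeric LDL summaries use only Friedewald LDL, from draws that need not be fasting, although direct LDL is measured in the same panel

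*SAP*

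**What the plan says.** - **Collection.** Protocol 6.5.1 lists the panel as follows: "Nonfasting lipid panel: total cholesterol, high-density lipoprotein (HDL), direct low-density lipoprotein (LDL), and triglycerides". The Protocol Appendix 2 footnote adds: "Fasting is not required for the lipid panel". The schedule in SAP Appendix 1 carries the same footnote.
- **Calculation.** SAP 7.2 computes LDL "using Friedewald formula when cholesterol, high-density lipoprotein(HDL), and triglyceride for a given blood drawn are available". Availability of the three components is the only condition. No fasting status is required and no triglyceride ceiling is set.
- **Choice of variable.** SAP 7.2 recognises that a measured value exists: "The third generation LDL is a direct measurement from blood drawn. Both generations of LDL will be listed in the listing". It then states: "Only fourth generation LDL calculated from the Friedewald formula will be used for analysis". It gives no reason for preferring the calculated value.
- **Numeric summaries.** SAP 7.2.1 plans baseline values, visit values and "Change from baseline at each postbaseline visit" by treatment group for selected tests, with no fasting restriction. The selected tests are not named. That LDL is among them is inferred from SAP 7.2.
- **Grading.** SAP 7.2.2 notes that the grading scale for triglycerides, calculated LDL and cholesterol applies to fasting values, "so nonfasting lipid results (or lipid results without a known fasting status) will not be graded or summarized by toxicity grades".

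**The concern.** Triglycerides enter the formula with a negative sign, so a triglyceride rise unrelated to LDL, such as one after a meal, can lower the analysed LDL. The plan accepts nonfasting draws throughout and sets no limit at which the formula stops being used. The direct value contains no triglyceride term and comes from the same panel, but it goes only to listings.

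At stake is the readability of the LDL summaries by group and visit. They may carry avoidable scatter. If triglycerides or meal timing shift over the study, or differ between arms, part of an apparent LDL change could come from the formula.

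**Working it through.** The documents give no LDL figure to reproduce, no size for a post-meal triglyceride rise, and no fasting mix by visit or group. The inputs below, other than the formula, are therefore assumptions shown over a range.

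**Step 1: error in a single value.** From SAP 7.2, LDL = TC − HDL − TG/5 (mg/dL). Let triglycerides rise by d while true LDL and HDL stay the same, and let total cholesterol rise by c·d. I assume c lies between 0 (total cholesterol does not move) and 1/5 (it moves in the ratio the formula itself implies). Then

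error = c·d − d/5 = −(1/5 − c)·d.

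| Assumed TG rise d | c = 1/5 | c = 0 |
|---|---|---|
| 25 | 0 | −5 |
| 50 | 0 | −10 |
| 100 | 0 | −20 |
| 150 | 0 | −30 |

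**Step 2: error in change from baseline.** Let q0 be the share of baseline draws taken after a meal and q1 the share at follow-up. Take the largest case, c = 0, with the same rise d for everyone and meal status independent between visits:

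- mean error in change = −(q1 − q0)·d/5
- SD of that error = (d/5)·√[q0(1 − q0) + q1(1 − q1)]

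For d = 50, d/5 = 10:

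| q0 | q1 | Mean error | SD of error |
|---|---|---|---|
| 0 | 1 | −10 | 0 |
| 1 | 0 | +10 | 0 |
| 0.3 | 0.7 | −0.4 × 10 = −4 | 10 × √0.42 = 6.5 |
| 0.5 | 0.5 | 0 | 10 × √0.50 = 7.1 |
| 1 | 1 | 0 | 0 |

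Everything scales with d. The extreme mean error is 5 mg/dL at d = 25 and 20 mg/dL at d = 100, in either direction. The 50%/50% case keeps a mean error of 0, with an SD of 3.5 and 14.1 respectively. Any c above 0 shrinks all of these, and c = 1/5 removes them.

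**Step 3: group contrasts.** The error in a between-group difference in change is the difference between the two groups' mean errors. If both groups go from 30% to 70% post-meal with d = 50, it is −4 − (−4) = 0. If only one group does so and the other stays at 50%/50%, it is −4 − 0 = −4.

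**Step 4: the same steps with direct LDL.** The TG/5 term is absent, so this source of error is 0 at every d, q0 and q1.

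**The case against.** The case for leaving the plan alone has real substance.

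- **Grading is protected.** SAP 7.2.2 keeps nonfasting and unknown-status lipids out of the toxicity-grade tables. This stands in full. It does not reach the numeric summaries in SAP 7.2.1, where the same values enter without restriction.
- **The stakes are low.** SAP 7.2 plans no formal testing of laboratory data, LDL is neither an endpoint nor a named objective, and the direct value remains visible in listings. This stands and sets the severity.
- **Total cholesterol may move with triglycerides.** The formula rearranges to TC = LDL + HDL + TG/5. With illustrative LDL 120 and HDL 50, triglycerides of 100 imply TC 190, and triglycerides of 300 imply TC 230; calculated LDL stays at 120. Only if TC is held at 190 does it fall to 190 − 50 − 60 = 80. So the one-fifth effect is an upper bound.

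A reader might go further and infer that LDL changes from baseline are biased downward, or that a treatment-related triglyceride rise would show up as a fall in LDL. The documents do not support either. Bias in change needs a shift in meal status or triglycerides between visits, it can run in either direction, and nothing is reported about such shifts. The second statement also needs total cholesterol to rise by less than one-fifth of the triglyceride rise, so the most that can be said is that it could happen.

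A reader might also infer that the SAP departs from a protocol-specified analysis. It does not: Protocol 6.5.1 says what is collected, and Protocol 8.6.3 does not say which LDL value is analysed.

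**Conclusion.** The point holds as a minor one. The plan bases its LDL analysis on a calculated value from draws that need not be fasting, without a triglyceride limit, while a direct measurement is available and no reason is given for setting it aside.

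The error in a single calculated value is 0 to 30 mg/dL for assumed triglyceride rises of 25 to 150 mg/dL, depending on how far total cholesterol rises with them. For the numeric summaries the expected consequence is added noise. Bias in change from baseline arises only if meal status or triglycerides shift between visits, and bias in group contrasts only if they differ by arm. The sizes rest on the assumed rises, on c lying between 0 and 1/5 and, for the change-from-baseline figures, on a common rise and meal status independent between visits.

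The exposure is limited to descriptive numeric LDL summaries. The graded laboratory tables and the primary endpoint are not affected.

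**What to change.** In SAP 7.2, name the direct (third generation) LDL as the variable for numeric summaries and change from baseline. Keep the Friedewald value in listings, or analyse it only for samples with documented fasting. The fasting-only route would not do as the main analysis, because the protocol does not require fasting draws and few values might qualify.

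The cost is a change of analysis variable and the matching SAP wording. No new sample or assay is needed, since the direct value is already in the protocol panel and already planned for the listings. If the sponsor prefers to keep the calculated value, the SAP should give the reason and label the numeric summaries as calculated LDL from draws of any fasting status.

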7.2.1. Summaries of Numeric Laboratory Results

Descriptive statistics will be provided by treatment group for selected laboratory test as follows:

- Baseline values
- Values at each postbaseline visit
- Change from baseline at each postbaseline visit

A baseline laboratory value will be defined as the last measurement obtained on or prior to the date/time of first dose of study drug. Change from baseline to a postbaseline visit will be defined as the visit value minus the baseline value. The mean, median, Q1, Q3, minimum, and maximum values will be displayed to the reported number of digits; SD values will be displayed to the reported number of digits plus 1.

Median (Q1, Q3) of the change from baseline values for these selected laboratory tests will be plotted by treatment group and visit.

In the case of multiple values in an analysis window, data will be selected for analysis as described in Section 3.8.3.

7.2.2. Graded Laboratory Values

The DAIDS Table for Grading the Severity of Adult and Pediatric Adverse Events, Version 2.1 dated July 2017, will be used to assign toxicity grades (0 to 4) to laboratory results for analysis. Grade 0 includes all values that do not meet the criteria for an abnormality of at least Grade 1. For laboratory tests with criteria for both increased and decreased levels, analyses for each direction (i.e., increased, decreased) will be presented separately.

For triglycerides, LDL (4th generation), and cholesterol, the toxicity grading scale is for fasting test values, so nonfasting lipid results (or lipid results without a known fasting status) will not be graded or summarized by toxicity grades.

7.2.2.1. Treatment-Emergent Laboratory Abnormalities

Treatment-emergent laboratory abnormalities are defined as values that increase at least 1 toxicity grade from baseline at any postbaseline visit, up to last exposure date for subjects who permanently discontinued study drug, or the last available date in the database snapshot for subjects who were still on treatment at the time of an interim analysis. If the relevant baseline laboratory value is missing, any abnormality of at least Grade 1 observed within the time frame specified above will be considered treatment emergent.

7.2.2.2. Summaries of Laboratory Abnormalities

Laboratory data that are categorical will be summarized using the number and percentage of subjects in the study with the given response at baseline and each scheduled postbaseline visit.

The following summaries (number and percentage of subjects) for treatment-emergent laboratory abnormalities will be provided by lab test and treatment group; subjects will be categorized according to the most severe postbaseline abnormality grade for a given lab test:

- Graded laboratory abnormalities
- Grade 3 or 4 laboratory abnormalities

For all summaries of laboratory abnormalities, the denominator is the number of subjects with nonmissing postbaseline values.

A by-subject listing of treatment-emergent laboratory abnormalities and treatment-emergent Grade 3 or 4 laboratory abnormalities, respectively, will be provided by subject ID number and visit in chronological order. This listing will include all test results that were collected throughout the study for the lab test of interest, with all applicable severity grades and abnormal flags displayed.

7.3. Body Weight and Vital Signs

Descriptive statistics will be provided by treatment group for body weight, BMI and vital signs as follows:

- Baseline value
- Values at each postbaseline visit
- Change from baseline at each postbaseline visit

A baseline value will be defined as the last available value collected on or prior to the date/time of first dose date of study drug. Change from baseline to a postbaseline visit will be defined as the postbaseline value minus the baseline value.

In the case of multiple values in an analysis window, data will be selected for analysis as described in Section 3.8.3. No formal statistical testing is planned.

A by-subject listing of vital signs will be provided by subject ID number and visit in chronological order. Body weight, height, and BMI will be included in the vital signs listing, if space permits. If not, they will be provided separately.

7.4. Prior and Concomitant Medications

Medications collected at screening and during the study will be coded using the current version of the World Health Organization (WHO) Drug dictionary. The WHO preferred name and drug code will be attached to the clinical database.

7.4.1. Nonstudy Drug Antiretroviral Medications

Any nonstudy drug ARV medications are defined as any ARV medications taken prior to, during, or after the study (if collected). All nonstudy drug ARV medications will be listed. No inferential statistics will be provided.

7.4.2. Concomitant Non-ARV Medications

Concomitant non-ARV medications are defined as non-ARV medications taken while a subject took study drug. Use of concomitant medications from Study Day 1 up to the last exposure date will be summarized (number and percentage of subjects) by treatment group, WHO drug class and preferred name. Multiple drug use (by preferred name) will be counted only once per subject. The summary will be sorted alphabetically by drug class and then by decreasing total frequency within a class. For drugs with the same frequency, sorting will be done alphabetically.

If the start or stop date of non-ARV medications is incomplete, the month and year (or year alone, if month is not recorded) of the start or stop date will be used to determine whether the non-ARVs are concomitant or not. The medication is concomitant if the month and year of the start or stop (or year of the start or stop, if month is not recorded) of the medication does not meet either of the following criteria:

- The month and year of start of the medication is after the last exposure date
- The month and year of stop of the medication is before the first dose date of study drug

If the start and stop date of non-ARV medications are complete, the start date is not after last exposure date and the stop date is not before first dose date, or the non-ARV medications are marked as ongoing and start date is on or before last exposure date, the non-ARV medications are concomitant.

Summaries of non-ARV concomitant medications will be based on the Safety Analysis Set. No formal statistical testing is planned. A by-subject listing for all non-ARV concomitant medications will be listed and sorted by subject ID number and administration date in chronological order.

